# **5.3.** Computing Environment

All statistical analyses will be performed using validated SAS statistical software Version 9.4 (or later), unless otherwise noted.

#### **5.4.** Baseline Definitions

### Baseline definitions applied to double-blind (DB) period:

For 24-hour urine PD parameters, baseline will be defined as the median of all valid 24-hour urine PD parameters collected prior to the first dose date/time of study drug (lumasiran or placebo). Baseline for other PD parameters will use the mean of all measurements collected prior to the first dose date/time of study drug (lumasiran or placebo).

For other parameters, baseline is defined as the last non-missing value prior to the first dose date/time of the study drug (lumasiran or placebo), unless otherwise specified. The baseline value for any measurements with multiple values at a visit (e.g. ECGs, height and weight for patients <18 years old) will be defined as the mean of the latest values collected prior to the first dose date/time of study drug.

### **Baseline definitions applied to During Lumasiran Treatment:**

For patients randomized to lumasiran, baseline as defined above for the double-blind period will be used.

For patients randomized to placebo who took at least one dose of lumasiran in the extension period, baseline for all parameters [except for 24-hour urine PD parameters] will be defined as above but the date of the first dose date/time of study drug will be the first date/time of lumasiran dose. For 24-hour urine PD parameters, the baseline will be defined as the median of all valid assessments at month 6. If the subject does not have two valid 24-hour urine PD assessments at month 6, then the baseline will be calculated based on the latest three valid 24-hour urine PD collections prior to the first dose date/time of lumasiran.

### 5.5. Randomization Stratification Factors

The mean 24-hour urinary oxalate excretion ( $\leq$ 1.70 mmol/24h/1.73m^2 or >1.70 mmol/24h/1.73m^2) from the first 2 valid 24-hour urine collections during screening will be the stratification factor. The stratification factor will be recorded in both the IRS (Interactive Response System) and the clinical database.

The central laboratory for the 24-hour urinary oxa	alate measurements used for randomization
during screening was transitioned from	(i.e., Clinical Assay) to
(i.e., Validated PD assay). As a result, the first 5 s	
on the Clinical Assay	and the remaining patients were stratified
using the results based on the Validated PD Assay	y

The planned statistical methods will adjust for baseline 24-hour urinary oxalate (refer to Section 5.4 and Section 7.1) and may not match the stratification factors as recorded in IRS. Any discrepancies will be summarized.

# **5.6.** Multiple Comparisons/Multiplicity

The family-wise Type I error control for the primary and secondary endpoints will be achieved by the gatekeeping testing strategy. Once the primary hypothesis testing is statistically significant at a 2-sided 0.05 significance level, the secondary endpoints will be tested in the following hierarchical order.

- 1. Absolute change in 24-hour urinary oxalate corrected for BSA from baseline to Month 6
- 2. Percent change in 24-hour urinary oxalate: creatinine ratio from baseline to Month 6
- 3. Percent change in plasma oxalate from baseline to Month 6
- 4. Proportion of patients with 24-hour urinary oxalate levels at or below 1.5xULN at Month 6
- 5. Proportion of patients with 24-hour urinary oxalate levels at or below ULN at Month 6
- 6. Absolute change in plasma oxalate from baseline to Month 6

Only if the comparison is significant at a 2-sided 0.05 significance level will the next endpoint in the hierarchy be formally tested; if a given comparison is not significant at a 2-sided 0.05 significance level, the subsequent tests will be performed, and the results will be summarized, but statistical significance will not be inferred.

# 5.7. Missing Data

Patients who discontinue the study prior to Month 6 will be encouraged to remain on study and complete their remaining clinical visits (excluding PK assessments) through the visit at Month 6 and only safety follow-up visits afterwards. All data collected regardless of whether it was collected before or after treatment discontinuation will be used for analysis. However, it is possible that data will remain missing.

An AE will be considered treatment emergent unless it can be unequivocally determined (from the partial onset date and/or a partial or complete stop date) that the event occurred prior to first dose of study drug.

For medications with partial start or stop dates: the first day/month will be imputed for start date, and the last day/month will be imputed for stop date. For medications with a completely missing start date, the medications will be considered as started prior to the first dose of study drug in this study; medications will be classified as prior or both prior and concomitant depending on the medication stop dates. If any medications have a completely missing stop date, then the medication will be assumed as ongoing.

### 5.8. Visit Windows

For table and figure summaries of the DB period, all data will be tabulated and analyzed per the evaluation visit as recorded on the electronic case report forms (eCRF) even if the assessment is outside of window.

For table and figure summaries of the during lumasiran treatment, the data collected at study visits during the extension period will be re-mapped for the patients randomized to placebo to reflect the visit relative to the first dose of lumasiran (e.g. Month 7 re-mapped to Month 1), Month 8 re-mapped to Month 2, etc.).

Unless otherwise specified, data collected at an unscheduled visit will be included in by patient listings and/or spaghetti plot figures, but no assignment of the scheduled visit will be made for the purposes of summary tabulations. However, unscheduled study visits will be used in the calculation of baseline values and for the any categorical shift tables (e.g. shift from baseline to worst post-baseline value).

### 5.9. Interim Analysis

There will not be an interim analysis prior to the primary analysis of the 6-month double blind period which will occur when the last patient completes the 6-month visit. There may be interim analyses conducted after the 6-month double-blind period to support regulatory and/or publications requests.

# 5.10. Analysis for Primary Endpoint and Database lock

As this study will be ongoing at the time of the primary analysis, the study database will have an interim database lock occur (i.e. data in EDC will be frozen and external data such as laboratory data will be QA'd and cleaned) when the last patient completes the 6-month visit to conduct the primary analysis of the double-blind period. Additional details regarding the interim database lock are located in the study Data Management Plan. The study will then be unblinded and all data entered as of the date of the primary treatment phase database lock will included in the summary of the Clinical Study Report (CSR).

After the study is completed (i.e. all patients complete the long-term open-label extension period and/or required safety follow-up visit(s)), the database will be hard locked, and all data will be summarized in the updated CSR.

### 6. STUDY ANALYSES

# **6.1.** Patient Disposition

Number and percentage of patients will be tabulated for the following categories:

- Screen Failures
- Enrolled (signed informed consent and met eligibility)
- Randomized
- Treated
- Full Analysis Set (FAS)
- Safety Analysis Set
- PK Analysis Set
- All Lumasiran Treated Set
- Plasma Oxalate Analysis Set

Summaries of the number and percentage of patients who discontinued treatment, withdrew from study, and primary reasons for either discontinuation of treatment and/or withdrawal from study will be presented. Additionally, the number of patients who completed the month 6 visit will also be displayed. A patient is defined as having completed the month 6 visit if the patient has at least one valid 24-hour urinary oxalate corrected for BSA at that visit.

The number and percent of patients enrolled by country and site will be summarized by randomized arm and overall. The number and percent of patients in each randomization stratum recorded in IRS vs. clinical database will also be summarized by randomized treatment arm and overall.

Data listings of those patients who withdrew and/or discontinued treatment including the associated reasons will also be presented. A separate listing of screening failure patients with the associated reason for screen failures will be generated.

# 6.2. Demographics and Baseline characteristics

Descriptive statistics of demographic characteristics including but not limited to: age (years), age category (6 to <12, 12to <18,  $\geq$ 18 to <65 and  $\geq$ 65), gender, race, ethnicity, region, height, weight, BSA, and body mass index (BMI) will be presented. For patients <18 years at screening, modified z-scores for height, weight and body mass index will also be summarized.

Additional disease baseline characteristics including but not limited to: 24-hour urinary oxalate excretion corrected for BSA (mmol/24hours/1.73m²), 24-hour urinary oxalate: creatinine ratio, eGFR (mL/min/1.73m²), plasma glycolate ( $\mu$ mol/L), plasma oxalate ( $\mu$ mol/L), and total number of patients reported with vitamin B6 use prior to study entry will be summarized using descriptive statistics.

A tabular summary of historical disease characteristic information such as: age at diagnosis, time from diagnosis to first dose date (months), time from first symptoms to first dose date (months),

time from diagnosis to first symptoms (months), number of siblings with PH1, reported history of disease events (e.g. pyelonephritis, renal stones, kidney stones, urinary tract infection), and genotype will also be presented.

# **6.3.** Medical History

A complete medical and surgical history will be collected during screening. The medical and surgical history will be coded using the Medical Dictionary for Regulatory Activities (MedDRA; Version 21.1 or higher).

Medical and surgical history will be summarized for the Safety Analysis Sets by system organ class, high level term and preferred term.

### 6.4. Prior and Concomitant Medications

Prior and concomitant medications will be coded using the World Health Organization (WHO) Drug Dictionary (September 2018 or later). Prior medications are defined as medications that were taken prior to and stopped before the first dose of treatment (lumasiran or placebo). Concomitant medications are defined as medications which were taken prior to and were ongoing while on study drug or medication(s) taken on or after the first dose date of the study drug.

Tabular summary of the number and percentage of subjects taking concomitant medications will be summarized by anatomic therapeutic class (ATC) and preferred term. Data will be presented for the Safety Analysis Sets. A separate tabular summary of Prior Vitamin B6 and Concomitant Vitamin B6 use will be summarized by ATC and preferred term.

One subject/patient listing for prior medication/concomitant medications and a separate listing for prior and concomitant vitamin B6 medications will be generated.

# 6.5. Dosing and Extent of Exposure

Summaries of exposure will include the following categories such as, but not limited to: total number of doses received per patient, mean number of dosing per subject, cumulative number of doses received, duration of drug exposure (months), cumulative drug exposure time (months), the total dose administered (mg) and total volume administered (mL).

Definition of drug exposure (days) will be defined as the minimum of [Exposure time= (date of last exposure – date of first dose +1)] where date of last exposure will represent either the date of the last dose administered dose +84, analysis cut-off date or end of study date. The exposure during the DB period will be right censored; that is, the date of the last exposure will not be later than the first date of dosing in the Extension period.

Dose interruptions and compliance are not taken into account.

### 7. STATISTICAL ANALYSIS

# 7.1. Primary Endpoint

The primary endpoint of this study is the percent change from baseline to Month 6 in 24-hour urinary oxalate corrected for body surface area (BSA). The primary comparison between the randomized arms is based on the percent changes at months 3, 4,5, and 6 from baseline. The analysis will be conducted using the Full Analysis Set.

24-hour urinary oxalate (mmol/24hrs/1.73m^2) corrected for BSA at each visit per patient is calculated as follows:

[Urine oxalate concentration (umol/L)/1000 (umol/mmol)] \* [24hr urine volume (mL)/1000 (mL/L])] \* [24 hours/actual collection hours] \* [1.73/(BSA)]

where BSA=square root (mean height (cm)\*weight (kg)/3600) at the visit.

Only valid 24-hour urinary oxalate values will be included in the analysis (note: valid is defined as: creatinine ≥10.0 mg/kg, duration of collection 22 to 26 hours, no missing voids and the sample was not collected within 14 days after the most recent dialysis session, if applicable).

The primary analysis will be performed using a restricted maximum likelihood (REML) based Mixed-Effect Model Repeated Measures (MMRM) approach. The outcome variable is percent change from baseline in 24-hour urinary oxalate corrected for BSA (mmol/24hr/1.73m^2) at months 3, 4, 5, and 6. Analysis will include fixed effects of treatment arm (lumasiran vs. placebo) and scheduled visits (months 3, 4, 5 and 6), as well as continuous, fixed covariate of baseline 24-hour urinary oxalate corrected for BSA (mmol/24hr/1.73m^2) level and patient as a random factor. The treatment estimates from this model will represent an average percent change from baseline of 24-hour urinary oxalate excretion across months 3 through 6 at which the treatment effect is expected to have reached steady state. Furthermore, given the variability of 24-hour urinary oxalate, averaging the values across these visits will yield stable treatment estimates. An unstructured covariance structure matrix will be used to model the within-patient error. If the fit of the unstructured covariance structure matrix fails to converge, then the following covariance structures will be assessed: autoregressive (1), compound symmetry, and Toeplitz and the structure selected will be based upon the best fit chosen by Akaike Information Criteria (AIC). The Satterthwaite approximation will be used to estimate denominator degrees of freedom. At each visit, least square (LS) means with corresponding standard errors (SEM) and 95% confidence intervals (CI) will be displayed by treatment arm. The primary comparison is the LS mean treatment difference (lumasiran – placebo) in percent change from baseline of 24hour urinary oxalate excretion from months 3 to 6. This LS mean difference will be presented along with corresponding standard errors (SEMs), 95% CIs and p-value from the model.

Descriptive statistics will also be generated by treatment arm at each scheduled visit. LS Mean (+/- SEM) figures of percent reduction by treatment arm will be plotted as well as individual spaghetti plots. A table of the mean maximum percent reduction during the 6-months for each treatment arm will also be generated. It should also be noted that the primary measure (i.e., 24-hour urinary oxalate corrected for BSA), as well as other PD markers, is based on validated PD assay

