Formal statistical hypothesis testing will be performed on the primary and secondary efficacy endpoints evaluated during the DB period (except eGFR as this endpoint is not expected to change within six months). Testing will be conducted at the nominal 2-sided 0.05 level of significance. Secondary endpoints will be tested in a prespecified hierarchy (Section 5.6). Summary statistics will be presented, as well as 2-sided 95% confidence intervals on selected parameters, as described in the sections below.

All data recorded on the CRF will be displayed in data listings.

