### 7.1.1. Sensitivity Analysis

Sensitivity analysis will be conducted to evaluate the sensitivity to the estimated treatment effect by the assumption of lumasiran reaching steady state of the treatment effect at month 3 and maintained through month 6.

- Sensitivity analysis 1 estimates the treatment effect of the primary endpoint without assuming equal treatment effect from month 3 through month 6. The analysis adds the interaction of visit and treatment to the primary MMRM model, when month 3 through month 6 data are used.
- Sensitivity analysis 2, similar to sensitivity analysis 1, estimates the treatment effect of the primary endpoint without assuming equal treatment effect from month 3 through month 6, but including all post-baseline data (including percent change from baseline at months 1 and 2)).

**Table 1:** Analyses of the Primary Endpoint

Analysis	Analysis Set	Statistical model	Data 
Primary analysis	Full Analysis Set	MMRM (subject, baseline, treatment, visit)	M3, M4, M5, M6
Sensitivity Analysis 1	Full Analysis Set	MMRM (subject, baseline, treatment, visit, treatment*visit)	M3, M4, M5, M6
Sensitivity Analysis 2	Full Analysis Set	MMRM (subject, baseline, treatment, visit, treatment*visit)	M1, M2, M3, M4, M5, M6

<sup>1Percent change from baseline in 24-hour urinary oxalate corrected for BSA at each month (M) to be used in the model.

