# 7.2. Secondary Endpoints

For secondary endpoints assessed to Month 6, the analysis will compare randomized arms (lumasiran vs. placebo) using the Full Analysis Set. During the Double-Blind Period, data will be collected during Screening, Day 1 and Months 1, 2, 3, 4, 5 and 6 with the exception of eGFR which is also collected at Week 2. To control for type I error, the primary and selected secondary endpoints will be tested in a hierarchical order as described in Section 5.6.

Absolute change from baseline in 24-hour urinary oxalate corrected for BSA will be analyzed using an MMRM model as specified for the primary endpoint. The percent change in 24-hour urinary oxalate: creatinine ratio, the percent change and the absolute change in plasma oxalate from baseline to Month 6 will also be analyzed using a similar MMRM model to the primary endpoint with the exception being that the baseline variable will be the baseline value of the corresponding endpoint.

For the two plasma oxalate related endpoints, a separate enriched analysis set of patients (i.e., Plasma Oxalate Analysis set) will be used. The plasma oxalate analysis set is defined as those patients who received any amount of study drug and have a baseline plasma oxalate level  $\geq$  1.5\*LLOQ. The LLOQ of the plasma oxalate assay is 5.55 µmol/L. Because it is not

possible to quantify plasma oxalate levels below LLOQ using the assay, patients with baseline plasma oxalate levels near the LLOQ (i.e. <1.5\*LLOQ) are excluded from the analysis to ensure that meaningful reductions in plasma oxalate can be evaluated for the study population.

For binary endpoints, i.e., the proportion of patients with 24-hour urinary oxalate  $\leq$ 1.5 ULN and  $\leq$  ULN at Month 6 the number and associated percent of patients who met each threshold at Month 6 will be presented by treatment arm. Refer to Appendix A for the value of ULN. Binary endpoints will be analyzed using a Cochran-Mantel-Haenszel (CMH) test stratified by baseline urinary oxalate ( $\leq$ 1.70 mmol/24hr/1.73m² vs. >1.70 mmol/24hr/1.73m²). The odds ratio with the corresponding 95% confidence interval and associated p-value will be presented. In addition, the differences in proportion of responders and corresponding 95% confidence interval using the Newcombe method based on the Wilson score will also be presented.

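### As specified, the primary MMRM (unstructured matrix, one common treatment effect, Satterthwaite df) rejects a true null about 8% of the time at N=30 instead of 5%, and its 95% CI covers about 92%

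*SAP*

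**What the plan says.** SAP Section 7.1 specifies a REML repeated-measures model for percent change in 24-hour urinary oxalate at Months 3, 4, 5 and 6. Its fixed effects are treatment, visit and baseline. Table 1 in Section 7.1.1 lists the primary model as "MMRM (subject, baseline, treatment, visit" with no treatment-by-visit term; only the two sensitivity analyses add one. For the covariance: "An unstructured covariance structure matrix will be used to model the within-patient error". AR(1), compound symmetry and Toeplitz are considered only if that fit fails to converge, with the choice made by AIC. For inference: "The Satterthwaite approximation will be used to estimate denominator degrees of freedom". The same paragraph also adds baseline "level and patient as a random factor". No adjustment of the standard error for estimating the covariance matrix is named.

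Section 5.2 sets the level: "Testing will be conducted at the nominal 2-sided 0.05 level of significance". Section 5.6 makes the primary test the gate to six ordered secondary tests: "Only if the comparison is significant at a 2-sided 0.05 significance level will the next endpoint in the hierarchy be formally tested". Section 7.2 analyses absolute change in urinary oxalate "using an MMRM model as specified for the primary endpoint" and uses a similar model for the oxalate:creatinine ratio and both plasma oxalate endpoints. The plasma endpoints are analysed in the subset with baseline plasma oxalate at least 1.5 times the LLOQ.

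**The concern.** With one treatment coefficient and an unstructured matrix, generalised least squares does not average the four visit differences equally. It weights them by the inverse of a 4×4 matrix whose 10 parameters are estimated from about 30 patients. The model standard error takes the weights as known. Satterthwaite changes only the reference degrees of freedom and leaves that standard error as it is.

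Two things are at stake. First, the headline 95% interval is too narrow and the primary p-value is not a 5% test. Second, the error carries into the hierarchy. Percent change in plasma oxalate is third. If the urinary tests before it pass and lumasiran has no effect on plasma oxalate, the rejection rate of that single test is the family-wise error.

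It is also unclear which covariance model supplies the p-value. A random patient effect is redundant beside an unstructured matrix, compound symmetry or Toeplitz, and estimable only beside AR(1). A literal run could be singular and set off the fallback for reasons unrelated to the data.

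**Working it through.** **Inputs from the documents.** Two-sided 5%, 37-point difference, SD 25 in each arm, 2:1 allocation, 24 patients for 90% power, 30 enrolled (protocol Section 7.1, SAP Section 5.1); model as above.

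**Inputs assumed.** Normal data; the between/within-patient split of the SD (20/15, 10/23, 24/7); Month 6 within-patient variance multiplied by 0.449, because it is a median of three collections; plasma set sizes below 30.

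**The plan's own figure.** Placebo n = (1.960 + 1.282)² × 25² × 1.5 / 37² = 7.2, so 8, and 24 in total. With 16:8 the noncentrality is 37 / (25 × √(1/8 + 1/16)) = 3.42, and noncentral-t power on 22 df is 90.4%. The 90% reproduces. That calculation is a two-sample t-test and says nothing about the size of the MMRM.

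**Mechanism in closed form.** With complete data, the common-effect model with an unstructured matrix is equivalent to regressing each patient's Month 3–6 mean on treatment, baseline and three within-patient visit contrasts that carry no treatment information. Put v = N − 3.

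- True variance is inflated by 1 + 3/(v − 4) = (v − 1)/(v − 4), the price of estimating three weights.
- The model variance is low by about (v − 3)/v and omits that inflation.
- Model SE / true SD ≈ √[(v − 3)(v − 4) / (v(v − 1))].
  - N=30, v=27: √(24×23 / (27×26)) = 0.887.
  - N=24, v=21: √(18×17 / (21×20)) = 0.854.
- Rejection rate: the Satterthwaite df is about v, so the cut-off is 2.052 at N=30. In true-SD units it is 2.052 × 0.887 = 1.82; on 24 df the two-sided tail is 8.1%. At N=24, 2.080 × 0.854 = 1.78, and on 18 df the tail is 9.3%.

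With complete normal data this does not depend on the covariance values.

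**Simulation of the specified test under a true null** (10,000 trials per setting, Monte Carlo SE 0.3 points; missing-data rows 3,000 trials, SE about 0.5):

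| Setting | Rejection | CI coverage | Model SE / true SD |
|---|---|---|---|
| 20:10, three SD splits | 8.2–8.4% | 91.6–91.8% | 0.87–0.88 |
| 16:8, three SD splits | 8.9–9.2% | 90.8–91.1% | 0.85 |
| 20:10, 5% / 10% of visits missing at random | 9.0% / 9.3% | – | – |
| Plasma-type data, 20:10 | 8.2% | – | – |
| Plasma-type data, 16:8 / 13:7 / 10:5 (assumed sizes) | 9.2% / 11.1% / 13.5% | – | – |

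A second simulation with a different REML algorithm (7,000 trials per size, within-patient correlation 0.5) gave 8.2% at N=30 (model SE 7.36, empirical 8.32, ratio 0.88) and 9.5% at N=24 (8.12 and 9.54, ratio 0.85). All unstructured fits without the random patient term converged, 106,000 of them in the first set.

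**Alternatives under the null:**

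| Analysis | 20:10 | 16:8 | Plasma-type settings |
|---|---|---|---|
| Interaction model, equal-weight contrast | 4.7–4.9% (4.9% with 10% missing) | 4.5–5.0% | 4.8–5.4% (Kenward-Roger) |
| Current model, Kenward-Roger | 5.5–5.9% | 5.5–5.9% | 6.8% at 13:7, 7.7% at 10:5 |
| Fallback: compound symmetry | 5.1–5.4% | – | – |
| Fallback: AR(1) | 7.0–8.4% | – | – |

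These rest on fewer trials (2,000–5,000 per setting for the interaction model, 4,000 for the fallbacks). In the second simulation Kenward-Roger on the current model gave 5.9% at N=30 and 6.1% at N=24, and the equal-weight contrast with Satterthwaite df gave 5.1% at N=30.

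**Cost in precision and power.** For the 20/15 split at 20:10 the SD of the equal-weight estimate is 8.25, against 8.85 for the specified one. At a true 37-point effect, power for the specified and the equal-weight test is 99.0% and 99.1% (20:10, 20/15), and 90.7% and 90.3% (16:8, 24/7).

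**Random patient term.** The rank of the covariance parameterisation with a patient variance added is 10 of 11 (unstructured), 2 of 3 (compound symmetry), 4 of 5 (Toeplitz) and 3 of 3 (AR(1)).

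**The case against.** - *A near-nominal analysis is already planned.* SAP Section 7.1.1: "Sensitivity analysis 1 estimates the treatment effect of the primary endpoint without assuming equal treatment effect from month 3 through month 6". Averaged equally over visits, that model has about 5% size. This stands as far as it goes, and it makes the fix cheap. But the SAP defines no equal-weight contrast there, and the sensitivity analysis does not replace the primary estimate, interval or p-value, nor does it cover the secondary tests.
- *The literal model was not fitted.* It includes the random patient term, and whether the redundancy would stop convergence was not shown. If compound symmetry were then chosen, the size would be near nominal. AIC selection and Toeplitz were not simulated. This stands, so the 8% is conditional on the unstructured matrix being fitted. That the size depends on this wording is itself a reason to change it.
- *N=24 is the powering number, not the analysis size.* Fair: the Full Analysis Set is everyone randomised and dosed, and 30 are planned. The N=30 figure is the main one.
- *The primary decision hardly moves.* Also fair. At N=30 the half-width is 2.052 × 7.36 = 15.1 points against 2.052 × 8.32 = 17.1, about 2 points short on a 37-point effect. The specified test alone is significant in 0.5–1.0% of trials at 20:10 and 1.1–2.7% at 16:8.
- *The larger plasma figures rest on assumed set sizes and normal data*, while values below the LLOQ are set to the LLOQ. They are illustrative. The 8.2% with all 30 patients needs no assumed set size.
- *Kenward-Roger alone keeps the protocol's mean model.* At N of 24 to 30 it removes most of the excess, but not all, and less in smaller sets.

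**Conclusion.** The concern holds. If the unstructured matrix is fitted as written, the primary test has a size of about 8% at N=30 (about 9% at N=24), and the 95% interval covers about 92% (about 91%). The closed form and both simulations agree. ANCOVA on the simple Month 3–6 mean kept its size in the second simulation (4.8% at N=30, 5.3% at N=24), so the excess comes from the estimated weights and not from the small sample alone.

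The target of estimation is not the problem. If the effect is constant over Months 3–6, the coefficient estimates the stated average; if it drifts, for example 30/35/40/43, the estimate moves at most 1.4 points from the simple average. The SAP justifies the model by the stability of averaging over visits, but the specified estimate is more variable than the simple average.

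This should be fixed, though it does not threaten the primary conclusion at the planned effect. The practical exposure is interval coverage and the continuous secondary tests: a family-wise error of about 8% through plasma oxalate if that endpoint is null, the urinary tests pass and all 30 patients qualify, and more in a smaller set, whose size the documents do not give. The figures assume normal data.

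**What to change.** 1. Make the Sensitivity Analysis 1 model primary: treatment, visit, treatment-by-visit and baseline, with an unstructured matrix.
2. Define the primary estimate as the contrast with weight 1/4 on each lumasiran-minus-placebo LS mean difference at Months 3, 4, 5 and 6, with Kenward-Roger standard error and df.
3. Delete the random patient factor wherever an unstructured, compound symmetry or Toeplitz matrix is used, in Section 7.1 and Table 1.
4. Use the same model and contrast for the four continuous secondary endpoints (Section 7.2) and for any subgroup interval taken from this model (Section 7.3).
5. Keep the no-interaction model as a sensitivity analysis. Kenward-Roger on the current model alone is a partial remedy.

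The cost is wording in SAP Sections 7.1, 7.1.1 and 7.2 and one contrast statement. Because protocol Section 7.2.5.1 states the same no-interaction model, the change also needs a justified entry in SAP Section 8 and in the study report, which SAP Section 1 provides for. No new data are needed, and power at the planned effect is essentially unchanged.
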